Residents attending the Canadian Orthopaedic Association (COA), Canadian Shoulder and Elbow Society (CSES) resident training course in Ottawa will be consented for participation. Once consented, residents will be randomized to one of two groups using a computerized blocked protocol based on year of study (R4 and R5) to assure equal level of training between control (technical surgical instructional video) and intervention (immersive VR) groups. Every participant will complete a demographic questionnaire to determine age, handedness, visual correction (eyeglasses), familiarity with shoulder surgery, number of previous courses attended, and familiarity with simulation training and VR. Within the demographic questionnaire will be six questions regarding confidence of performing a reverse shoulder arthroplasty using a modified confidence scale (CS). The demographic questionnaire format will be of Likert-scale responses.

The control group will receive training on completion of a reverse shoulder arthroplasty using a technical surgical instructional video. The control group will be provided as much time as they require to watch the video, including repetition if desired during which they will be timed for completion.

The intervention (VR) group will receive training on completion of a reverse shoulder arthroplasty using an immersive VR simulator (PrecisionOS Technology, Vancouver, BC, Canada). The VR simulator utilizes an HMD producing 3D visuals with haptic controllers for an immersive operating room experience. The module produced consists of the key steps in performing a reverse shoulder arthroplasty using virtual versions of the equipment used in the real procedure. Prior to initiation, participants will be provided with a safety and training demonstration on the use of the VR module by study personnel. The intervention group will similarly be provided as much time as they desire with available repetition as they see fit. The VR group will be timed to task completion as the control group for comparison.

The VR module will provide users with a score based on time to completion of key steps, and performance of key steps such as guide-pin insertion, and overall glenoid baseplate orientation. These positioning scores will be based on clinically relevant cut-off values seen to affect implant longevity. These scores will be subsequently compared to GRS and OSATS scores provided by the assessors for validation purposes.

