Both groups will then be taken to a technical skills laboratory where they will be paired with an assessor (fellowship trained, consultant shoulder surgeon and member of CSES). The assessors will be blinded to the training received by the participant. The participants from both groups will then complete a reverse total shoulder arthroplasty using the same equipment used in either the control (technical surgical instructional video) or intervention (VR) learning activity while being assessed on fresh frozen cadavers (scapula to hand). The assessor will use an OSATS, GRS, and overall competency assessment for the resident during the procedure and for evaluation of the finished product. The assessor will also time the resident for time to task completion, which will be determined by the resident when they explicitly express that they are satisfied with final implantation. Following this, participants will complete a survey assessing their enjoyment of learning activity, perceived benefit to continued use in learning orthopaedic skills, and a re-assessment of their confidence following training modality using the modified confidence scale (CS). The post-cadaveric questionnaire format will be of Likert-scale responses.

As part of the procedure, both the assessor and participant will determine implant parameters once the reverse shoulder arthroplasty is complete. The cadaveric specimens with inserted glenoid baseplates will be CT scanned to provide 2D and 3D reformats. This will allow for determination of the implant orientation parameters including version, inclination, rotation, and offset. These parameters will be compared to the VR scores to determine correlation between the VR training and real-world task completion.

Sampling Design and Subject Selection:

Subjects will be recruited from attendance at the Canadian Shoulder and Elbow Society (CSES) annual meeting by volunteering to participate. Subjects recruited will be in their PGY4 or PGY5 years of orthopaedic residency training and will be from multiple Canadian institutions. Once participants are recruited, study personnel will randomize groups to intervention (VR) or control (technical surgical instructional video) groups via a blocked randomization process in statistical computing software R (R Foundation for Statistical Computing, Vienna, Austria).

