A recent systematic review comparing validity assessments of surgical orthopaedic simulators demonstrates a breadth of cohort variability, with 17.7% to upwards of 50% differences in reported outcome measures between novice/intermediate and expert groupings. TER ratios have seen variations from 7-42% in early VR simulators for novice surgeons. These studies predominantly focus on VR simulators lacking the immersion of contemporary VR, particularly the system from PrecisionOS.

Similarly, the majority of VR simulator research in orthopaedics pertains to arthroscopic surgery which utilizes different global ratings scale outcome measures. The authors of this proposal have recently completed a similar randomized controlled trial at the 2019 CSES meeting (REB approval obtained from the University of Calgary) comparing senior resident VR training to traditional didactic scientific journal training. This resulted in a significant difference in cadaveric task completion time with n=8 in both groups. This study is presently pending publication and in review. As such, for power determination of comparison of VR trained to control group of novice surgeons utilizing a 2-sided test at 5% significance (alpha = 0.05) and to achieve 80% statistical power (beta = 0.02), considering a representative estimated difference of 25% (which we have seen in our previous study, and is conservative regarding similar literature) in combined outcome measures, six subjects will be required for each cohort.

Inclusion Criteria:

1. Individuals registered in licensed post-graduate orthopaedic residency programs attending the CSES resident course and consenting to participation.

Informed Consent:

There will be no direct patient interaction, therapeutic intervention, or other diagnostic or therapeutic intervention related to patient care. Participants will be provided with a consent form outlining the study. Information gathered on participants will not include direct identifiers aside from demographics of age, gender, and training experience. Questionnaires collected will be de-identified using study codes.

The research demonstrates minimal risk to subjects involved as per TCPS2 Chapter 2, and Chapter 10, as the proposed study is observational, does not allow for direct identification of patients, is not staged, and is non-intrusive.

Study Procedures

Randomization: Subjects will be blocked randomized based on year of study (R4 or R5) using computer software.

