Primary outcome of comparison of VR to technical surgical instructional video teaching will be assessed by OSATS, GRS, and competency grade provided by evaluators during the sawbone session. Secondary outcomes will be determined using the ToT and TER, overall time difference of task completion between groups, and CER. The cadaveric scapula will be assessed for implant version, inclination, rotation, and offset in the glenoid and recorded for each participant using a CT scan.

Data collection sheet including measures assessed can be seen in appendix.

Analytical Plan

Normality testing will be performed via Shapiro-Wilk test with subsequent mean comparative statistics to determine difference between VR and control groups. Descriptive statistics will be conducted. Likert questionnaire responses will be treated as Likert-scale and Likert-type data using descriptive statistics. Reliability testing for outcome scales in determining internal consistency will be assessed by Cronbach's alpha.

Ethical considerations

Potential Benefits: Study participants will receive expert instructional information regarding shoulder arthroplasty by participating. No remuneration for participation will occur. Longitudinal benefits could include improved technical skills in reverse shoulder arthroplasty.

Potential Risks: No direct risks to study participants involved. Subject recruitment is free of coercion, and only de-identified demographic data used with adherence to FIPPA and TCPS2 guidelines for data handling and storage.

Subject Safety Provisions: No direct risks to study participants. Occasionally use of immersive VR can produce feelings of nausea. This will be dictated to study participants prior to commencing the study, and participants are free to withdraw at any time. Safety provisions include data handling and transfer of patient information with adherence to FIPPA and TCPS2 guidelines and all attempts to store and utilize de-identified data.

Ethics Approval: Fraser Health Research Ethics Board (REB); Calgary REB

Plans for Publication and conference presentations:

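### Should the cadaver time comparison be tied to the pass/fail grade, given that the resident stops the clock?

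*Combined protocol and SAP*

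**What the plan says.** Under Study Design, the assessor times the cadaver procedure and the resident decides when it ends: "time to task completion, which will be determined by the resident when they explicitly express that they are satisfied with final implantation". Quality is recorded separately for every resident: "The assessor will use an OSATS, GRS, and overall competency assessment for the resident during the procedure and for evaluation of the finished product". The Research Objectives make the competency assessment a pass/fail judgement, and assessors do not know which training the resident had.

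Under Measures, quality comes first: "Primary outcome of comparison of VR to technical surgical instructional video teaching will be assessed by OSATS, GRS, and competency grade". Time is secondary: "Secondary outcomes will be determined using the ToT and TER, overall time difference of task completion between groups, and CER". The Analytical Plan is brief: "Normality testing will be performed via Shapiro-Wilk test with subsequent mean comparative statistics to determine difference between VR and control groups". The Research Objectives say that efficiency is to be judged by transfer of training (ToT) and the transfer effectiveness ratio (TER).

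No available text makes time conditional on passing, censors or replaces the time of a failed procedure, or plans a joint reading of time and grade. The data collection sheet that the Measures section places in an appendix is not in the available text.

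**The concern.** A resident who stops early with a poor implantation contributes a short time, and the time comparison as written rewards this. If such residents were concentrated in one arm, that arm could look faster because it did worse. With six residents per arm, one or two such results move a mean visibly.

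A reading of time on its own is conceivable. The research question pairs efficiency with competency, and the sample size text cites cadaver time as the notable result of the group's previous trial: "This resulted in a significant difference in cadaveric task completion time with n=8 in both groups". At stake would be a statement that one training method makes residents faster when it only makes them stop sooner.

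**Working it through.** **Inputs.** From the sample size text: six residents per arm, two-sided test at 5%. The plan gives no procedure time, standard deviation or failure rate, so it has no figure of its own to reproduce here. Assumed: mean time 60 minutes, coefficient of variation (CV) 15%, 25% or 35%, normal times, and a two-sample t test as the reading of the planned mean comparison. A failed resident takes a share f of the usual time.

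**Step 1: shift of the arm mean.** With k failures among six, the mean falls by k(1 − f)/6.
- f = 0.5: 0.5/6 = 8.3% for one failure, 1.0/6 = 16.7% for two.
- f = 0.8: 0.2/6 = 3.3% and 0.4/6 = 6.7%.
- f = 1.2 (slow failures): the mean rises by 3.3% and 6.7%.

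Example: four residents at 60 minutes and two failures at 30 give (4 × 60 + 2 × 30)/6 = 50, against 60 in the other arm. With equal numbers of failures the shifts cancel.

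**Step 2: how often the arm with more failures is significantly faster when true times are equal** (40,000 simulated trials per cell; nominal rate 2.5% in that direction).

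| Failures, arm v arm | f | CV 15% | CV 25% | CV 35% |
|---|---|---|---|---|
| none | – | 2.5% | 2.5% | 2.5% |
| 1 v 0 | 0.5 | 3.9% | 4.9% | 4.7% |
| 2 v 0 | 0.5 | 11.0% | 10.6% | 9.2% |
| 1 v 0 | 0.8 | 4.3% | 3.7% | 3.4% |
| 2 v 0 | 0.8 | 7.9% | 5.7% | 4.7% |
| 2 v 0 | 1.2 | 0.3% | 0.8% | 1.2% |
| 2 v 1 | 0.5 | 0.2% | 1.5% | 2.3% |
| 1 v 1 | 0.5 | 0.0% | 0.3% | 0.9% |

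With failures occurring at random, 30% v 10% gives 9.5/8.0/6.7% at half time and 5.9/4.5/4.0% at 80% of usual time across the three CVs. At 20% v 20% and half time it is 2.6% throughout. Clear inflation therefore needs failures that are both fast and markedly unequal.

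**Step 3: what the safeguards would buy.**

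*Giving failed residents the longest observed time and requiring the same sign.* For 2 v 0 half-time failures at CV 15%, false findings fall only from 10.7% to 10.4% (a separate run from the table). The two short times also widen the spread, so the raw test tends to reach significance when the other four residents are quick by chance, and the sign then survives. For random 30% v 10% half-time failures the check does more: 7–10% falls to about 4%.

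*Also requiring a pass rate that is not lower.* False findings in the 30% v 10% half-time case fall to 0.2–0.3%. The cost is large. With equal failure probability p, the chance that a given arm has more failures is (1 − ΣP(k)²)/2 for a binomial with six trials. This is (1 − 0.418)/2 = 29.1% at p = 0.1 and (1 − 0.291)/2 = 35.5% at p = 0.2. For a true 25% time advantage (the planning difference), CV 15% and failures at ordinary times, correct findings fall from 84% to 59% at p = 0.1 and 54% at p = 0.2.

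*Ranking failures worst in the main test.* With three residents per arm in each year, one failure confined to one arm leaves that arm a best rank sum of (1+2+3) + (1+2+6) = 15 against an expected 21. The smallest two-sided p is then 36/400 = 0.09, so that arm could not reach significance.

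**The case for a change.** The strongest reply is that the primary outcome protects less than it seems. At six per arm a test on the grade would seldom flag an imbalance: Fisher's exact p is 0.45 for 2 v 0 failures, 0.55 for 3 v 1 and 0.18 for 3 v 0. A significant time difference could stand beside a non-significant competency result. The sign can even reverse. Take 3 v 1 failures that are 30% faster, a usual time of 100, and passing residents in the worse arm 10% slower. The worse arm then averages (3 × 110 + 3 × 70)/6 = 90, against (5 × 100 + 70)/6 = 95. With failure probabilities of 1/2 v 1/6 and failures 30–50% faster, the worse arm is significantly faster in 8–18% of simulated trials.

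The arithmetic stands, and so does the point that protection rests on seeing the counts rather than on a test. The premise does not stand: no section says failures will be fast or unequal. The one relevant piece of evidence, in the background on the previous trial, is that the VR group had a shorter dissection time together with better instrument handling scores. That is group-level evidence and cannot exclude individual fast failures, but it does not support the feared pattern either. ToT and TER are given without formulas, so whether they would inherit the problem cannot be determined.

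Two wording matters touch this point. The phrase for completing the task also describes training time ("The VR group will be timed to task completion as the control group for comparison"), although the Study Design and sample size sections attach it to the cadaver procedure, which is the natural reading for the secondary outcome. The efficiency objective names a manufacturer document as comparator, whereas the control arm receives a video. That inconsistency is separate and alters nothing here.

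**Conclusion.** The plan is silent on failed residents' times, but no change follows. Time until the resident declares satisfaction is a complete, defined secondary measurement, and comparing its means is legitimate. The information needed to read it properly, the number passing in each arm, is already due under the primary outcome, so an analyst will naturally set the two side by side. The plan does not announce an efficiency claim from cadaver time alone.

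The possible distortion runs from below the nominal 2.5% to about 11% for up to two failures in an arm, and to 18% under the more extreme assumed failure rates. All of these figures rest on assumed times, spreads and failure rates. Replacing failed times gains almost nothing in the two-against-none case and a moderate amount when failures are random and unequal, so it is an optional extra. The pass-rate condition protects well but gives up roughly 25 to 30 of every 84 correct findings (84 − 59 and 84 − 54). That is a debatable trade-off, not a correction of an error.

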Production of an immersive VR suite with haptic and user metric feedback would be an advance over current bench top simulator technology, allowing for greater immersion and interaction, leading to better understanding of surgical planning and implementation. The development of this technology could provide trainees with immersive levels of training not previously seen, with improved learning of technical skills over media such as manufacturer technical documents. The effectiveness of training and efficiency of training of the novel immersive VR training systems need to be evaluated as they are increasingly incorporated into competency based, contemporary residency education.

Research Question: Can immersive VR improve the efficiency and competency of technical skill acquisition in senior orthopaedic surgery residents over technical surgical instructional video in learning reverse shoulder arthroplasty?

Research Objective(s):

Primary: To determine if immersive VR is superior to technical surgical instructional video teaching in acquisition of technical skills in learning reverse shoulder arthroplasty

Technical skill outcomes will be determined by Objective Structured Assessment of Technical Skills (OSATS), a Global Ratings Scale (GRS), and competency assessment (pass/fail) by fellowship trained subspecialty shoulder surgeons

Secondary: (1) To determine the efficiency of learning of immersive VR compared to manufacturer specific technical instructional document training of senior residents in learning reverse shoulder arthroplasty.

1. Efficiency will be determined by transfer of training (ToT) and transfer effectiveness ratio (TER)
2. To validate a created VR scoring system with real-world performance (this will include the use of CT scans of cadaveric specimens)

METHODS

Study Design:

A randomized, blinded intervention-control trial directly comparing immersive VR versus technical surgical instructional video training for teaching of reverse shoulder arthroplasty to senior orthopaedic surgery residents will be conducted.

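### The CT part of the VR-score validation correlates raw implant position with a performance score; for any parameter with a target or two-sided range, a valid score can show a correlation near zero

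*Combined protocol and SAP*

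**What the plan says.** The second numbered item under the secondary objectives (Research Objective(s)) is "To validate a created VR scoring system with real-world performance", and it names CT scans of the cadaveric specimens as part of that work.

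The VR side is described in Study Design: "The VR module will provide users with a score based on time to completion of key steps, and performance of key steps". Guide-pin insertion and baseplate orientation are given as examples. On the positioning part it adds: "These positioning scores will be based on clinically relevant cut-off values seen to affect implant longevity". The cut-offs themselves are not listed. Participants may repeat the module as often as they wish.

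The CT side is also in Study Design. The scans allow "determination of the implant orientation parameters including version, inclination, rotation, and offset". The one analysis then stated is "These parameters will be compared to the VR scores to determine correlation between the VR training and real-world task completion".

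The Measures section repeats that the four parameters are recorded for each participant. The Analytical Plan lists a normality test, mean comparisons between groups, descriptive statistics and Cronbach's alpha. It names no correlation coefficient. No section gives a target, an absolute deviation or an in-range indicator for the CT values.

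Study Design also gives a second validation route: the VR scores are to be compared with the assessors' GRS and OSATS scores.

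**The concern.** The two sides of the planned correlation are different kinds of measurement. The VR score says how well the resident did, and its positioning part is built from cut-offs, so it rewards being in an acceptable place. A CT value such as version says where the implant is. If a parameter is best at a target or inside a range, errors to either side are both poor placements but sit at opposite ends of the CT scale. A linear or rank correlation of raw position with quality then partly or wholly cancels. The cut-offs that would put the CT result on a quality scale are tied to the VR module only.

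At stake is the CT part of a secondary objective. A low coefficient could be read as evidence against a score that works. A high one would have a sign and size that depend partly on which side of target the residents happened to fall. Two further gaps bear on interpretation. The score mixes time with positioning, and the plan does not say which component or which of several runs enters the correlation.

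**Working it through.** **Inputs from the documents.** There are four CT parameters and one statement that they are correlated with the VR scores (Study Design). Six subjects are required per cohort, with a two-sided 5% level (Sampling Design and Subject Selection). Only the VR group is described as receiving a VR score, so there are about six pairs. The plan gives no figure of its own for this correlation, so there is none to reproduce.

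**Assumptions (not in the documents).** Skill s ~ N(0,1). The VR score equals s, so it is valid by construction. The CT deviation from target is d = b + σ(s)·e, with e ~ N(0,1), σ(s) = 5·exp(-0.5s) degrees and b a fixed offset. The 5 degrees and the slope 0.5 are illustrative.

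**Step 1: errors centred on target (b = 0).**
- Raw: e has mean zero at every skill level, so Cov(s, d) = 0 and r = 0.00.
- Absolute deviation: r = -0.5·exp(0.125)·√(2/π) / √(exp(0.5) - (2/π)·exp(0.25)) = -0.452 / 0.912 = -0.50.
- Simulation agrees (0.00 and -0.50). Spearman's coefficients are 0.00 and about -0.45.

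**Step 2: 3-degree offset unrelated to skill (b = 3).** Simulated raw r = 0.00; absolute-deviation r = -0.41.

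**Step 3: offset that also shrinks with skill,** d = exp(-0.5s)·(3 + 5e). With k = 3/5 = 0.6, raw r = -0.5·k·exp(0.125) / √(exp(0.5)·(1 + k²) - k²·exp(0.25)) = -0.340 / 1.334 = -0.25. Absolute-deviation r = -0.50. With k from 0.5 to 3, raw r runs from -0.21 to -0.77.

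**Step 4: a score that is exactly minus the absolute deviation.** Correlation with absolute deviation is -1.00 throughout. Raw r depends on the mean offset:

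| Mean offset (SD) | Raw r |
|---|---|
| 0 | 0.00 |
| 0.25 | -0.32 |
| 0.5 | -0.58 |
| 1 | -0.86 |
| 2 | -0.99 |

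The same perfect score gives anything from 0.00 to -0.99. In samples of six centred on target, the middle 95% of raw r runs from about -0.99 to 0.99. About 27% of samples pass |r| > 0.81, roughly half with each sign.

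**Step 5: one-sided cut-off.** For a pass/fail score with a single limit at +0.5 SD, raw r = -φ(0.5) / √(Φ(0.5)·(1 - Φ(0.5))) = -0.352 / 0.462 = -0.76. Here the raw value does carry the information.

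**Step 6: precision with six pairs (Pearson).**
- Critical |r| = t/√(n - 2 + t²), with t(0.975, 4 df) = 2.776: 2.776/√(4 + 7.71) = 0.81.
- Observed r = 0.70: atanh(0.70) = 0.867; 1.96/√3 = 1.132; limits tanh(-0.264) and tanh(1.999), that is -0.26 to 0.96.
- Under the Step 1 model, the absolute-deviation correlation reaches p < 0.05 in about 16% of trials with six pairs and 24% with eight.

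**The case against.** **The wording is loose.** The plan says the parameters are compared with the scores. It does not say signed values, name a coefficient or exclude scoring the CT result first, and the team may intend to apply the module's cut-offs to the CT data. This is fair, but no such step is written. The literal text correlates the parameters themselves, so one added sentence is needed on either reading.

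**Symmetry is not stated.** The documents mention cut-offs, not targets or ranges. A one-sided limit is equally compatible and gives a non-zero raw correlation (Step 5). Offset is not an angle, and rotation may have no meaningful target. This stands: the point applies parameter by parameter, only where there is an optimum or a two-sided range.

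**Near-zero is one scenario.** If errors lie to one side and better residents err less, raw r is negative (Step 3). This also stands. A reader might infer that any non-zero raw r is spurious. In Step 3 it is not, because better performers do err less. The difficulty is that raw r alone cannot separate that case from the others.

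**The objective has another route.** A reader might conclude that this secondary objective is bound to get a wrong answer. The documents do not support that: CT is only one part of it, and the GRS and OSATS scales rise with quality and have no target-value problem.

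**The fix gains little at this size.** About 16% power is low. That is a reason for a more modest claim, but not for keeping a metric that can be blind to what it is meant to detect. Six is also the calculated requirement, not a stated cap.

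**Conclusion.** The point holds in a conditional form. As written, the plan correlates implant position with a performance score and never puts the CT values on a quality scale. For a parameter with a target or two-sided range, a valid score can then show r = 0.00 where absolute deviation shows -0.50, or -0.41 with a fixed 3-degree offset. These sizes rest on an assumed model. The two-sided premise is inferred from the cut-off wording and would fail for a one-sided limit.

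The reach is limited to the CT part of one secondary objective. The GRS and OSATS comparison and the primary comparison between arms are untouched. Separately, about six pairs cannot support a claim of validation by CT even with the right metric. The change is worth making before the data are analysed.

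**What to change.** 1. For each CT parameter, define a quality measure in advance: either the CT result scored with the same cut-offs as the VR module, or its absolute deviation from the module's own reference. The investigators set both. Where a cut-off is one-sided or a parameter has no meaningful target, say so and treat it accordingly. Keep the raw values as descriptive.
2. Correlate that measure with the VR positioning component from one run named in advance, where the module records it; otherwise use the overall score. The documents do not say whether components or individual runs are stored, so this needs checking.
3. Report Spearman's coefficient with a 95% CI, and state that only the VR arm contributes.
4. Reword the CT part of the objective as exploring the association between VR score and implant position.

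Cost: wording only, with no new specimens or scans. Direction of error is kept only descriptively, and the claim becomes more modest. Absolute deviation is not a complete remedy: if all residents share a large offset unrelated to skill, its correlation with a valid score also weakens (simulated r = -0.31 for an offset equal to the error SD at average skill, and -0.14 for twice that).

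### The only sample-size statement pairs 80% power with beta = 0.02 and cannot be reproduced; at a 25-point difference, six per arm gives under 20% exact power on the pass/fail primary measure (Fisher or t-test)

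*Combined protocol and SAP*

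**What the plan says.** All references are to the combined protocol and SAP.

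- **Sampling Design and Subject Selection** holds the only sample-size justification. It specifies "utilizing a 2-sided test at 5% significance (alpha = 0.05") and aims "to achieve 80% statistical power (beta = 0.02), considering a representative estimated difference of 25" per cent "in combined outcome measures, six subjects will be required for each cohort". The support offered is the authors' earlier trial at the 2019 course. For that trial the section reports a significant difference in cadaveric completion time with eight per group, but no mean or SD.
- **Research Objective(s), Primary** names OSATS, a GRS and a "competency assessment (pass/fail) by fellowship trained subspecialty shoulder surgeons".
- **Measures** repeats the list: "Primary outcome of comparison of VR to technical surgical instructional video teaching will be assessed by OSATS, GRS, and competency grade". It singles out none of the three and gives no rule for combining them.
- **Analytical Plan** provides for Shapiro-Wilk testing "with subsequent mean comparative statistics to determine difference between VR and control groups". It names no specific test, and none suited to a binary grade.

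**The concern.** There are three problems.

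1. Power is 1 minus beta, so the two stated figures cannot both be right.
2. A sample size for a difference in means needs an SD, and one for a difference in proportions needs a control rate. Neither is given, the test is not named, and the outcome to which the 25% applies is undefined. A reader therefore cannot get from the stated inputs to six per arm.
3. One of the three primary measures is binary. Six against six carries very little information on a pass rate, yet the plan's general claim of 80% power invites the reader to apply it to every primary measure.

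At stake is how the result is read. If the pass/fail comparison is non-significant with 12 residents, a stated power of 80% would make that look like evidence of no benefit, which it would not be.

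**Working it through.** **Inputs from the protocol:** two-sided alpha 0.05; power 80% and beta 0.02; difference 25%; n = 6 per arm. **Not given, so assumed over a range:** SD, control pass rate, test, and whether 25% is absolute or relative.

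**Step 1. Power and beta.** 1 − 0.80 = 0.20, and 1 − 0.02 = 0.98. The stated pair is inconsistent.

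**Step 2. Trying to reproduce six per arm on a continuous scale.** With no SD the calculation cannot be run forwards. It can be solved backwards for the standardised difference d that six per arm detects.

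- Normal approximation: d = (z for alpha + z for power) × √(2/n). At 80% power, (1.960 + 0.842) × √(2/6) = 1.62.
- Two-sample t-test: noncentral t with 10 df and noncentrality d × √(6/2). At 80% power, d = 1.80.

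For a 25% difference, the largest SD that fits is 25/d, as a percentage of the reference mean:

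| Target power | d, t-test | Largest SD | d, normal approx. | Largest SD |
|---|---|---|---|---|
| 80% (beta 0.20) | 1.80 | 13.9% | 1.62 | 15.5% |
| 98% (beta 0.02) | 2.58 | 9.7% | 2.32 | 10.8% |

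T-test power at six per arm for a 25% difference, by assumed SD:

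| SD (% of mean) | 12.5 | 13.9 | 15 | 20 |
|---|---|---|---|---|
| Power | 88% | 80% | 74% | 50% |

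Six per arm could therefore be right for OSATS or GRS, but nothing in the protocol shows that it is.

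**Step 3. Pass/fail grade, six against six.** Each arm can have 0 to 6 passes, so there are 7 × 7 = 49 possible results. Exact power is the sum of the binomial probabilities of the significant ones.

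Fisher's exact test (two-sided) is significant only for 0 v 5 (p = 0.015), 0 v 6 (p = 0.002), 1 v 6 (p = 0.015) and their mirror images. Gaps of four residents miss: 0 v 4, p = 0.061; 1 v 5, p = 0.080; 2 v 6, p = 0.061. So a gap of at least 5 of 6 residents is needed.

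Power over every control rate from 0 to 75% with a 25-point difference:

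| Test | Minimum | Maximum |
|---|---|---|
| Fisher's exact | 0.5% (control 0% or 75%) | 2.9% (control about 37.5%) |
| t-test on 0/1 data | 14.7% (control about 37.5%) | 19.7% (control about 10% or 65%) |

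The t-test row is the nearest reading of the planned comparison of means. If 25% means a relative increase, the maxima fall to 1.1% (Fisher) and 12.3% (t-test).

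**Step 4. What Fisher's test could detect with six per arm.**

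- If no control resident passes, power is the chance that at least 5 of 6 VR residents pass. At a VR rate of 86% this is 6 × 0.86⁵ × 0.14 + 0.86⁶ = 0.80. A true gap of about 86 points is the smallest that gives 80% power. A comparison of 5% v 95% gives 88%.
- If every VR resident passes, power is the chance that at most 1 of 6 controls passes: (1 − c)⁶ + 6c(1 − c)⁵ for control rate c. This falls below 80% once c exceeds 14.0%. Above that control rate, no higher VR pass rate reaches 80% power.

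**Step 5. Size that 80% power would need.** By the usual two-proportion formula, a 25-point difference needs 27 to 62 per arm, depending on the control rate.

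**The case against.** **Beta = 0.02 is probably a dropped digit.** Likely so, since 80% stands beside it. But the text does not settle which value was used, and correcting it leaves the other two problems in place.

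**The protocol does not claim 80% power for the pass/fail grade.** This is the strongest objection, and it stands as a limit. The 25% is attached to a combined measure, so Step 3 does not recompute the sponsor's own figure. It shows that a listed primary measure has no power justification of its own and very low power at the only effect size stated. The 25-point reading and the control rates are assumptions, although the whole possible range of control rates was covered.

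**The pass/fail figure depends on the test.** It does. Besides the two tests tabulated, maximum exact power is 11.5% by Boschloo's test, 19.6% by Barnard's and 19.7% by the uncorrected chi-square. The normal-approximation formula gives about 24% at the boundary rates, where exact chi-square power is 16.9%. An unpooled Wald test reaches 29%, but its true type I error goes up to 14.6%. The t-test on 0/1 data itself has a type I error of up to 6.8%, so 19.7% is generous. None of these is near 80%.

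**Six may be a minimum.** The protocol sets no cap, and the earlier trial had eight per arm. The figures here apply to six per arm, the number the protocol justifies.

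**Restating the claim as d = 1.80 is solved backwards from n = 6.** True. It says what the trial can detect. It supports the size only when set against an SD or an explicit range of SDs, which is why the fix asks for one.

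**Conclusion.** The concern holds and should be corrected before the plan is relied on. The power statement contradicts itself, and six per arm cannot be derived from what is written. For OSATS or GRS the size is unverifiable: adequate by t-test if the SD is no more than 13.9% of the reference mean, and down to 50% power if it is 20%. These SDs are assumptions. For the pass/fail grade at a 25-point difference, six per arm gives at most 2.9% power by Fisher's test and 19.7% by a t-test on 0/1 data, whatever the control rate. A non-significant result on that grade would tell the reader almost nothing.

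**What to change.** Keep the sample and the three primary measures, and reword the power paragraph.

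1. Correct beta to 0.20. The sponsor should confirm that 80% was the power used; if it was 98%, the stated power must change instead, and the detectable d at six per arm becomes 2.58.
2. Restate the claim, for example: *With 6 residents per arm and a two-sided alpha of 0.05 (two-sample t-test), the trial has 80% power (beta = 0.20) to detect a standardised difference of 1.80 on [OSATS or GRS, whichever is named].*
3. Give the SD for that scale and the source of the 25%. If no SD is available, say so and show power over a stated range of SDs, as in Step 2.
4. Define the combined outcome or remove the term.
5. Add: *The pass/fail competency grade is not powered at a 25-point difference; a non-significant result on it is not evidence of no benefit.* Naming the test for this grade in the Analytical Plan would complete the correction.

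The cost is one reworded paragraph and a sentence or two. No participants are added. The downside is a less favourable power claim, and, if no SD is on hand, one that rests on an openly assumed range.
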